5.0 END OF STUDY CONSIDERATIONS

5.1 Study Completion

A participating subject will be considered to have completed the study if and only if:

- He/she completed the treatment/intervention course described in this protocol
- He/she has complied with all the procedures and completed the two required blood draws within the allowable window
- He/she finished the exit survey

5.2 Voluntary Withdrawal of Consent

Subjects shall have the ability to withdraw consent for study participation and/or the use of their clinical information at any time and for any reason, without penalty or loss of benefit to which the subject is otherwise entitled, by contacting the Principal Investigator or a designated member of his research team, preferably in writing and addressed to the Principal Investigator at the address indicated on the cover page of this protocol.

In the case a subject enrolled in this study decides to withdraw from the research, or an Investigator decides to terminate a subject's participation, study investigators must follow accepted standard practices regarding the management of collected data about these subjects, as follows:

- Investigators must document in the research record each instance of a subject withdrawal, including the reasons for the withdrawal, if known.
- If the subject withdraws and does not consent to continued follow-up and collection of clinical information, the investigator(s) will discontinue access to the subject's medical record or other confidential records, for purposes related to the study.
- Following the subject's withdrawal from the study, the Study Team will no longer contact the subject nor have access to his/her medical records for research purposes (unless specific informed consent has been obtained as described above).

5.3 Early Termination

The study sponsor or Principal Investigator of the study may decide to suspend or terminate a study for various reasons, including but not limited to the occurrence of an unanticipated problem, evidence of noncompliance, or serious adverse events and/or continuing noncompliance. If this occurs, the subject's designated Research Coordinator will send a certified letter to the patient explaining unsuccessful attempts were made to contact the patient to gain compliance and will therefore be terminated from the study. The Principal Investigator or an appointed study staff member will then notify the IRB in writing within three days of the suspension/termination. This communication will include a description of what steps have or will be taken to protect the welfare of currently enrolled participants, and what corrective actions, if applicable, will be taken to address the root cause for the suspension/termination.

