2.0 STUDY OBJECTIVES/PURPOSE OF THE STUDY

The purpose of this study is to assess the effect of using CGM versus a standard of care (e.g. traditional fingerprick protocol) in an at-risk, diabetic patient population. The impact will be measured in terms of clinical outcomes (e.g., HbA1c level, glycemic variability), health care utilization (inpatient/outpatient visits), self-reported patient perceptions, and costs. We expect that CGM will empower patients to better manage their diabetes—ultimately, improving their health and reducing the burden of disease.

Figure 1

In this study, patients with type I and II diabetes will record their blood glucose levels since the output of the Dexcom G6 and the Contour Next ONE measure interstitial glucose. However, as noted in the *3.0 Study Design*, although the American Diabetes Association has provided a conversion table in which $\text{blood glucose} = 28.7 \times \text{A1C} - 46.7$ [6], the current standard of care is to have patients directly measure their blood glucose in the clinic rather than approximating. Thus, patients enrolled in this study will track their glucose with the general hypothesis being that those who more consistently monitor their blood glucose levels (and avoid the high peak to valley changes), will have a lower HbA1c at the end of the study. This will be tested by having HbA1c levels measured at two distinct time points: (1) at the time of enrollment, and (2) at the end of the pilot (six months). HbA1c levels may also be checked at the study midpoint (three months) if determined to be current standard of care by the provider and this data will also be considered. The aims below are written for HbA1c to confirm to the current standard of care.

Aim 1: Assess impact of CGM on glycosylated hemoglobin levels

Specific Aim 1a (primary analysis): Measure the effect of CGM vs. standard finger-prick protocol on HbA1c

- **Hypothesis for Aim 1a:** The patient-level six-month reduction in HbA1c will be greater among those randomized to CGM than that among those randomized to standard finger-prick protocol.
- **Process for Aim 1a:** We will compare the distributions of the patient-level, six-month change in HbA1c between randomized groups using the two-sided Wilcoxon rank-sum test.

Specific Aim 1b: Measure the longitudinal change in mean amplitude of glycemic excursion (MAGE) in CGM

- **Hypothesis for Aim 1b:** The patient-level daily MAGE will decrease over six months of CGM.

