3.2 Number of Subjects

We aim to recruit 125 patients, expecting 20% attrition by the six-month follow-up, yielding about 100 patients for analysis (see *7.2 Sample Size and Power*).

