7.1 Statistical Considerations

The primary analysis (Aim 1a) will measure the intervention effect on the patient-level six-month absolute reduction in mean HbA1c. Since not all patients will have their final HbA1c test at six months exactly, we will estimate each patient's six-month reduction in HbA1c by interpolating/extrapolating from their assessments, given that their HbA1c levels were assessed on at least two occasions: baseline, and >3 months post baseline. Then, among patients with a sufficient number of occasions of HbA1c assessments, we will estimate their sixmonth HbA1c using generalized linear mixed models with patient-level random slopes and intercepts, with appropriate link function and distributional family [8]. The quantitative secondary analyses (Aims 1b-e, 2a-b) will use outcomes related to the longitudinal change in various metrics of glycemic variability (MAGE, C_v , range) as well as the frequency of hypoglycemic events, healthcare utilization, and cost. The secondary analyses will also use longitudinal data analysis to assess whether there is a significant reduction in glycemic variability over six months (Aims 1b-d) among those randomized to CGM, whether there is a significant reduction in hypoglycemic events over six months (Aim 1e) among those randomized to CGM, and to assess whether overall healthcare utilization and costs differ between randomized groups [9]. Accordingly, specific aims 1b-e will rely heavily on longitudinal data analysis within a multilevel/hierarchical framework [10], specifically using generalized linear mixed models. In the sensitivity analyses, provider variability will be accounted for using three-level (provider, patient, occasion), quasi-Bayesian generalized linear mixed models [11]. Finally, the sensitivity analyses exploring HTE will use generalized additive models (GAM) to identify subgroups of patients for whom CGM is likely to have a differential effect [12-13].

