7.2 Sample Size and Power

Based on 2018 data pulled from Intermountain's diabetes registry, we estimate that the four RPC clinics (Cottonwood FM, Cottonwood Sr, Holladay IM, and Avenues IM) will see about 30, 22, 17, and 6 study-eligible, unique patient encounters per month, respectively, yielding up to about 75 recruitable patients per month (up to 225 over three months of enrollment). We estimate that enrolling 125 patients – expecting 20% attrition by the sixth-month follow-up, yielding 100 patients for analysis – would be sufficient to achieve >80% power for the primary analysis (absolute reduction in HbA1c) if the standardized difference d of the effect size is >0.8 (**Figure 2**). Here, the standardized difference d is measured in terms of the difference between the randomized group-level means of six-month changes in HbA1c. So, for example, a standardized difference d in the effect size of 0.8 might be observed if the true effect size is, say, -1 (that is, if the difference between the means is -1) and the standard deviation of change is 1.25. Details of the power analysis will be made available upon request.

[figure not shown]

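### Terminating unreachable noncompliant patients, with follow-up ending by default, leaves a primary analysis of retained patients with a late HbA1c and not of all randomized patients

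*Combined protocol and SAP*

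**What the plan says.** All references are to the combined protocol and SAP.

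- **Section 5.3** begins with suspending or terminating a study, and lists noncompliance among the possible reasons. It then turns to the individual patient, who is sent a certified letter "explaining unsuccessful attempts were made to contact the patient to gain compliance and will therefore be terminated from the study".
- **Section 5.2** introduces its data rules as covering both a subject's own withdrawal and an investigator's decision to end a subject's participation. After that, "the Study Team will no longer contact the subject nor have access to his/her medical records for research purposes", with an exception where specific informed consent was obtained.
- **Section 5.4** caps contact attempts for noncompliance at three, after which a certified letter may be sent. Patients who are reached again can return; those who are not are classed as lost to follow-up.
- **Section 7.1** estimates the six-month HbA1c reduction for patients "given that their HbA1c levels were assessed on at least two occasions: baseline, and >3 months post baseline".
- **Sections 2.0 and 3.2**: Aim 1a compares the six-month "change in HbA1c between randomized groups using the two-sided Wilcoxon rank-sum test", and the plan recruits 125 patients, "expecting 20% attrition by the six-month follow-up, yielding about 100 patients for analysis".

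No section states that patients are analysed as randomized whatever their adherence, gives a method for patients without a late HbA1c, or provides for a six-month HbA1c after termination.

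**The concern.** Read in sequence, these rules let a patient's conduct after randomization decide whether the primary outcome is ever observed. A patient stops supplying data, does not answer, is terminated, and by default can no longer be contacted or looked up. Unless a qualifying HbA1c already exists, that patient is outside the primary analysis.

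The trigger can work differently in the two arms. Section 4.2 has CGM readings upload automatically, whereas control patients take finger-prick readings that are synced by Bluetooth or, if that fails, entered by hand or reported to the coordinator. Sections 4.2 and 6.1 tie additional contact to missing data entry. Randomization does not protect a comparison from losses that arise this way.

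At stake is the meaning of Aim 1a, which is framed as a contrast between randomized groups. Aims 2a and 2b could also be affected, because visits and costs over six months would be truncated for any patient whose record access had ended.

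**Working it through.** **1. The plan's own figures.** Enrolment: 125 × (1 − 0.20) = 100, which reproduces Section 3.2. For power, Section 7.2 gives an example "if the difference between the means is -1" and "the standard deviation of change is 1.25", so d = 1/1.25 = 0.8. Alpha and allocation ratio are not stated; I assume 0.05 two-sided and 1:1.

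- 50 per arm: SE = 1.25 × √(2/50) = 0.25; 1/0.25 = 4.00; power ≈ Φ(4.00 − 1.96) = 97.9%. With a Wilcoxon efficiency of 0.955 it is 97.4%. Both agree with the stated figure of more than 80%.
- 62.5 per arm (all 125 followed): SE = 0.224; power ≈ 99.4%.

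Recovering the lost patients barely changes power at d = 0.8. The issue is bias.

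**2. Which planned draws satisfy Section 7.1.** Section 3.0 has a baseline draw, an elective draw at 3 months ± 1 week, and a required final draw (± 2 weeks). The elective draw qualifies only if it is taken and falls after the three-month mark. Otherwise only the final draw does. A patient terminated before then, with record access ended, will usually not qualify.

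**3. Illustration of bias.** The inputs below are assumptions, not figures from the documents, except the SD of 1.25 and the 20% average attrition. Let the true effect be 0, let a share d of an arm be excluded, and let excluded patients' mean HbA1c change be worse by δ than that of retained patients. Setting the whole-arm mean change to 0:

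0 = (1 − d)m + d(m + δ), so the retained mean is m = −dδ.

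Bias (CGM minus control) = −(d_CGM × δ_CGM − d_ctl × δ_ctl). Negative values favour CGM.

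SE = 1.25 × √(1/n_CGM + 1/n_ctl), with n = 62.5 × (1 − d). For 30%/10%, n = 43.75 and 56.25, so SE = 0.252.

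| Excluded, CGM/control | Bias, δ = 0.5 | Bias, δ = 1.0 | Type I error |
|---|---|---|---|
| 20%/20% | 0 | 0 | 5.0% |
| 25%/15% | −0.05 | −0.10 | 5.5% to 6.8% |
| 30%/10% | −0.10 | −0.20 | 6.8% to 12.5% |
| 10%/30% | +0.10 | +0.20 | 6.8% to 12.5% |

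Equal rates are no guarantee. With 20% excluded in each arm but δ = 1.0 in CGM and 0.5 in control, bias = −(0.20 × 1.0 − 0.20 × 0.5) = −0.10.

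**4. Scale.** A bias of 0.10 to 0.20 is 10% to 20% of the 1-point difference in the power example. It is 18% to 36% of the 0.55-point difference from the telehealth meta-analysis cited in Section 1.1 (0.10/0.55 and 0.20/0.55).

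**The case against.** A reader might infer that noncompliant patients are systematically removed and that the trial becomes a comparison of compliers. The documents do not support that.

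- **Analysis criterion.** Section 7.1 admits patients by HbA1c availability. Compliance is never a condition. Section 5.1 defines study completion partly by compliance, but that definition is not linked to any analysis set. A non-adherent patient with a late HbA1c is analysed.
- **Termination.** Section 5.3 is discretionary and begins at study level. The letter concerns patients who could not be reached; non-adherent patients who stay in contact are not removed by this text. Section 5.4 lets re-contacted patients return.
- **Record access.** The bullets in Section 5.2 speak of withdrawal, and their reach to termination rests on the lead-in sentence. One bullet ends access only if the subject withdraws and does not agree to continued follow-up, and specific consent is an exception. The consent pages are not available for this review, so whether such consent was sought cannot be checked.
- **Secondary aims.** The two-assessment rule does not apply to Aims 2a and 2b. Any effect there depends on how Section 5.2 is read.
- **Direction and size.** The 20% is overall attrition, not a rate of termination for noncompliance. Nothing in the documents shows that more CGM than control patients would be lost.

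All of this stands, and it limits the point. It does not remove it. Being unreachable after failing to supply data is still post-randomization behaviour, loss of access is still the default, and nothing is specified for patients without a late HbA1c.

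**Conclusion.** The concern holds in this form: the primary contrast is among retained patients with a late HbA1c, retention depends partly on behaviour that can differ by arm, and the plan has neither an as-randomized rule nor a missing-data method. Bias in either direction is possible. Its size and sign cannot be derived from the documents.

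Under the assumptions shown (no true effect, SD 1.25, 1:1 allocation, 20% average attrition, excluded patients 0.5 to 1.0 points worse), bias is 0 if exclusion is equal and for similar reasons. It is 0.10 to 0.20 points with a 30%/10% split, with the sign set by which arm loses more. Power is not threatened.

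This should be changed because the loss is partly avoidable: Section 4.2 already draws HbA1c history, utilization and cost from the medical record.

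**What to change.** 1. **Reconcile Sections 5.2, 5.3 and 5.4** so that study termination, subject noncompliance, loss to follow-up and withdrawal of consent are four separate events, each with its own data rule.
2. **Keep outcomes.** State that noncompliance or non-response alone does not end outcome collection. Unless the patient withdraws consent to record use, still obtain the six-month HbA1c (the planned clinic draw, or a laboratory record if one exists), visits and costs. A laboratory value cannot be taken for granted, since Section 3.0 allows that the final draw may not be standard of care.
3. **Amend Section 7.1** to say that all randomized patients are analysed in their assigned group regardless of adherence. Name a missing-data method for patients still without a late HbA1c, and a sensitivity analysis that lets their change be worse than that of observed patients, by differing amounts in each arm.
4. **Report** the number without a late HbA1c by arm, with reasons.

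The cost is protocol and consent wording, a chart pull for the patients concerned, and an estimate that may turn out less favourable. The sample size need not change, and patients' right to withdraw is untouched. No rule on device resupply or on stopping the intervention is proposed.

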5.4 Lost to Follow-Up Subjects

Because this is a 13-month study, with periods of time between research-related interactions, retention of participating subjects until study completion could be a challenging element. To facilitate subject retention, specific information will be obtained during the first research encounter and updated at all subsequent encounters. Although critically important to the successful completion of the study, if a participant expresses concern and/or refuses to provide this information, they will be excluded from the research.

The following specific information will be collected and used for this purpose:

- Contact information of the participant (i.e. phone number, email)

This contact information will be stored in a secure database and will not be shared outside of the study-specific research staff. If a research participant becomes lost to follow-up, the research team will contact the subject or designated individuals named by the participant. A maximum of 3 telephone calls and/or email will be attempted for non-compliance purposes. If there is no response, an IRB-approved certified letter signed by the Principal Investigator requesting for a response may be sent. If contact is reestablished, interest in continued participation will be verbally confirmed and documented, and the participant will return to active study participation as appropriate, based on their status/time point in the research. With failure to re-establish contact after three direct attempts and a certified letter in the mail, and failure to find new contact information, the subject will be considered lost to follow up.

5.5 Records Retention

The Principal Investigator and his/her designated research staff are responsible for maintaining accurate, complete, and current records relating to the conduct of the investigation, in accordance with ICH Good Clinical Practice guidelines (E6) and the Code of Federal Regulations (CFR) (refer to ICH GCP 8.1 to 8.4 for a list of essential documents for retention).

6.0 MONITORING AND SAFETY REPORTING

6.1 Monitoring

Internal monitoring of the study will be done weekly by the research coordinators assigned to the study. He/she will verify the accuracy of recruitment, ensure complete data entry, etc. These results will be shared monthly with the Savvysherpa Chair, [name], in the form of an emailed report or available hyperlink which updates in real-time. If patients are not entering their data, the research coordinator may call/email the subject to remind them about this ask.

6.2 Safety Reporting

Since all devices used in this study are FDA approved and commercially available, it is anticipated that no safety reporting will be required. However, in the event of a safety issue, safety-related data for this study will be collected on standardized reporting forms (paper and/or electronic). Safety-related events will be defined in accordance with ICH GCP E6 R2, the Code of Federal Regulations, Intermountain research policy, Intermountain SOPs, and all current applicable regulations. These will be reported to the study Principal Investigator and Institutional Review Board within 24 hours. An issue would be tracked via REDCap from the Research coordinator and an alert triggered for key research personnel.

Study participants who have not previously used a CGM to monitor blood glucose levels are likely to have questions and/or concerns about their blood glucose levels. These are most likely to occur if blood glucose levels decline during sleep or following exercise. Participants will be instructed to call their primary care doctor for advice.

In the event any device recalls or new information pertaining to the safety/accuracy of the devices is obtained, the study team shall take appropriate action to ensure subject safety which will be delegated by the Principal Investigator.

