4.2 Methods

Patients will be screened for eligibility per Inclusion and Exclusion criteria (See Sections 3.3.1 and 3.3.2 respectively) and consented as described in Section 4.1.

The following information will be obtained from each subject's medical records, and/or during procedures, treatments, study-specific visits, and/or follow-up visits that are generally part of their usual or specialized care:

- Patient's ID number (EMPI)
- General demographic information (age, gender, height, weight, race, ethnicity)
- Patient's contact information (email, home address, and phone)
- Health history (personal health history, previous laboratory and glucose test results, medications, healthcare utilization and cost data)
- Current medications/medication history
- Glucose levels and historical A1c reports

Group #2 data will be transmitted from the Contour Next One device to the Contour mobile app via Bluetooth. Should this process fail, a contingency plan has been devised for patients to manually record their readings in an online REDCap form or provide their readings to their Research Coordinator who will properly store the data. Patients in the intervention group will have their data automatically uploaded via the Dexcom G6 app where it will then be obtained by Intermountain Healthcare researchers. No protected health information will be shared with those outside of this research study unless approved by the IRB. Coordinators will check in with the patients on a monthly basis (or more frequently for non-compliance) to ensure proper data entry and to answer any questions (if necessary).

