4.3 Risks

This study is low risk. The study uses FDA approved devices that are commercially-available to track glucose monitoring. The Intervention Group should experience less pain than the standard of care since they will not have daily finger pricks, and The Control Group is the current standard of care. As with all studies that involve data, there is always a risk that this could be shared, however, study-related information will be stored within Intermountain's system and applications that have been reviewed and approved by cybersecurity. Further, by using study ID number (e.g. Subject_001) rather than referring to PHI, we will minimize the risk of incidental disclosure.

The Dexcom G6 is a pressure sensitive acrylic adhesive coated on top of a polyester spunlace fabric. The plastic housing is attached to the patch by direct pressure and heat. There is no latex or bovine components in the adhesive however, if the patient has a severe acrylic or polyester allergy it is possible they may experience skin irritation or topical allergic reactions at the site of which sensor was applied.

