8.3 Data-Sharing with Collaborators

Deidentified data obtained from this study will be shared with Savvysherpa in accordance with signed legal documents to help develop predictive models for diabetes care. Data will be transferred using either SFTP or an encrypted hard drive and in accordance with cybersecurity approval.

Further, collected data will be transcribed into visualizations on a Tableau dashboard. The specific outputs will include recruitment totals for each particular site, patient demographics, glucose tracking, etc. No protected health information will be on the Tableau dashboard—it will serve as a real-time tracking tool for Intermountain senior leadership. Furthermore, [name], who specializes in diabetic management will be provided the dashboard link and he will interpret the CGM profiles on an interim basis. [name] will monitor subject safety within the data (Tableau) and report back any concerning findings to the study team and/or their respective Reimagine Clinic Provider. He will also regularly speak with the study team on his glucose monitoring results and data updates on a weekly basis.. This will ensure the safety of participants and be useful for developing future national standards on CGM diabetic care.

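### No scheduled contact or survey item is stated to ask about adverse events, so skin reactions and symptomatic events that leave no reading or visit are recorded only if volunteered, and the specialist's safety review is not tied to the safety record

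*Combined protocol and SAP*

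**What the plan says.** Section 6.2 starts from the devices being approved and on the market, and concludes that "it is anticipated that no safety reporting will be required". It then gives a route for a known problem: "in the event of a safety issue, safety-related data for this study will be collected on standardized reporting forms", with tracking and an alert through REDCap and a report to the principal investigator and the IRB within 24 hours. Participants with concerns about their glucose are told to call their primary care doctor.

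Section 4.3 names a risk specific to the CGM arm. Of patients who are severely allergic to the adhesive's materials it says "it is possible they may experience skin irritation or topical allergic reactions at the site of which sensor was applied".

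The planned contacts are described by purpose. In Section 4.2, "Coordinators will check in with the patients on a monthly basis (or more frequently for non-compliance) to ensure proper data entry"; the other stated purpose is answering questions. Section 3.0 has the coordinator resupply equipment each month. Under Section 6.1 the coordinators' weekly internal monitoring is to "verify the accuracy of recruitment, ensure complete data entry, etc". The exit survey in Appendix A covers diet, exercise, device helpfulness, self-rated health and willingness to take part again, and ends with an open comment box.

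Section 8.3 adds a safety review of the data. A diabetes specialist interprets the CGM profiles on an interim basis, watches subject safety on the dashboard, speaks with the study team weekly, and is to "report back any concerning findings to the study team and/or their respective Reimagine Clinic Provider".

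**The concern.** The Section 6.2 route handles an event that someone has already brought forward; it does not find one. If nobody is asked, the safety record depends on which patients speak up. A trial that records no skin reactions or symptomatic events under that arrangement has not shown that there were none.

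Two further matters follow. A comparison of lows between arms would partly reflect how closely each arm is observed. And a concern raised in the Section 8.3 review can be passed on in a way that satisfies the text without an entry in the Section 6.2 record.

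What is at stake is any safety statement made from this pilot, including one used to support wider use of CGM in these clinics. The HbA1c comparison does not depend on it.

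**Working it through.** The plan states no figure on this point, so the check is mainly a reading of the text: for each kind of event, which stated route would bring it into the study record without the patient raising it?

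**1. Does any scheduled contact ask?**
- Monthly check-in (4.2): data entry and answering questions. No adverse-event enquiry stated.
- Monthly resupply (3.0): equipment. None stated.
- Weekly internal monitoring (6.1): recruitment accuracy and data completeness, with an open-ended list. None stated.
- Exit survey (Appendix A): no item on skin, hypoglycemia or adverse events. Only free text could catch one. The survey also comes near the end of participation (3.0), so a patient who leaves early may not reach it.

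**2. Which events have another route?**
- *Sensor-site skin reaction.* Glucose data cannot show it. It is captured only if volunteered. It can occur only in the CGM arm, so the problem is under-capture rather than a biased comparison.
- *Low glucose with a reading.* Visible. CGM data upload automatically and control readings go by Bluetooth with a manual fallback (4.2). Aim 1e compares hypoglycemic events between arms, and Section 8.3 provides the specialist review.
- *Emergency visit or admission.* Counted under Aim 2a.
- *Symptomatic event with no reading and no visit,* such as a low treated at home with another person's help. Captured only if volunteered. Even where a reading exists, the glucose value does not record that help was needed or consciousness lost.

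**3. Is observation of lows equal by arm?**
- CGM: one reading every five minutes (Synopsis), so 24 × 60 / 5 = 288 readings a day.
- Control: the daily finger-prick regimen set by the physician (3.0). The number per day is not given. A control patient's low during sleep would usually leave no reading.
- The Section 8.3 review names CGM profiles for interpretation; finger-prick readings are not expressly named.

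**4. Does the review feed the record?**
Section 8.3 joins its two recipients by and/or, so telling the clinic provider alone meets the text. It does not refer to the Section 6.2 forms, REDCap tracking or 24-hour report, and Section 6.2 does not refer to it. Neither gives a rule for when a low seen in the data becomes a recorded safety event.

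**5. What would an empty record mean?** (illustration only)
Assume 1:1 allocation, which the documents do not state: 125 / 2 = 62.5, taken as 62 CGM patients. Let p be the true proportion with a skin reaction and s the share who volunteer it. Both are assumptions. The chance of recording at least one is 1 − (1 − p·s)^62.

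| p | s = 25% | s = 50% | all asked (s = 100%) |
|---|---|---|---|
| 2% | 26.7% | 46.4% | 71.4% |
| 5% | 54.2% | 79.2% | 95.8% |
| 10% | 79.2% | 95.8% | 99.9% |

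At p = 5%, 62 × 0.05 = 3.1 reactions are expected. The chance that none is recorded is 100 − 54.2 = 45.8% or 100 − 79.2 = 20.8% under volunteering, against 100 − 95.8 = 4.2% if all are asked. This shows how the meaning of a zero changes. It does not estimate the number missed in this trial.

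**The case against.** The strongest reply is that the plan does have safety provisions, that the devices are approved, and that this is a pilot. The opening sentence of Section 6.2 is an expectation, not a waiver: the next sentence sets up forms, event definitions by regulation and institutional procedure, prompt reporting and an alert. Some detail may sit in institutional procedures that are not part of these documents. All of this stands, and it limits the point to how events are found and where they are recorded.

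Several stronger readings are tempting, and the documents do not support them.

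- *Lows surface only if volunteered.* No. Device data, Aim 1e and the Section 8.3 review can all show them. Section 6.2 mentions falls in glucose during sleep or after exercise as prompts for questions; Section 4.3 does not list them as a risk.
- *A finding sent only to the provider never reaches the safety record.* No. The specialist speaks with the team weekly (8.3), and the clinicians are collaborators (3.3). What is missing is a stated link.
- *Patients who stop the sensor because of skin reactions would be filed as noncompliant.* No. Section 5.2 requires the reason for each withdrawal to be documented if known, and missing data should prompt contact. The gap is that nothing stated ensures the reason is asked for.
- *Sections 4.3 and 3.3.2 conflict on adhesive allergy.* No. Section 4.3 is a conditional risk statement and 3.3.2 is silent. Health history is collected (4.2), and the consent pages are not in the text reviewed.
- *A count of expected severe lows gives the size of the problem.* No. The documents give no such rate, and the calculation would count events that occur, not events that go unrecorded.

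It is also fair to say that a monthly question only partly offsets the difference in sampling between arms. It does equalize the enquiry about events that patients notice.

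**Conclusion.** The concern holds in a limited form. As written, sensor-site skin reactions and symptomatic events without a reading or a visit enter the record only if a patient raises them. Lows are observed far more closely in the CGM arm, and the Section 8.3 review has no stated path into the Section 6.2 record. An absence of reports, or a difference in lows between arms, could therefore not be taken at face value as a safety result.

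The number of events missed cannot be derived from the documents. The conclusion rests on the stated purpose of each contact and on the survey items as printed. It would weaken if coordinator scripts or institutional procedures outside these documents already required an adverse-event enquiry in both arms. The change is worth making because it is cheap and alters what the trial can say about safety.

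**What to change.** - **Section 6.2:** remove the expectation that no safety reporting will be needed, and keep the rest of the route.
- **Section 4.2 and Appendix A:** add a short fixed question set to the existing monthly check-in and the exit survey, worded identically in both arms: low glucose needing another person's help; loss of consciousness or seizure; emergency care; skin reaction; device stopped, and why. Record the answers in REDCap.
- **Section 7.0:** state that counts of these events will be reported by arm, noting that lows found in device data are observed more densely under CGM.
- **Section 8.3:** state that every concerning finding is also entered in the Section 6.2 record, whoever else is told, and cross-refer the two sections.

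The cost is a one-page REDCap form, wording in these sections, a few minutes per contact and more events to file. No new visits or staff are needed.
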